#### *Risks versus Benefits of the Proposed Research*

Given that most HIV-1-infected patients on effective ART have persistent low level viremia and despite this viremia have blunted HIV-1-specific immune responses, interventions with the potential to improve HIV-specific immunity and limit viremia should be tested. Therapies which improve HIV-1-specific immune responses will likely be a necessary component of any HIV remission or eradication strategy. Based on the data outlined above there is sufficient expectation that the proposed study will show an improvement in HIV-specific immune responses and the potential for latency reversal such that this result would advance the field. Although participants in this early phase study will receive no direct benefit for their participation in this study, there remains a strong desire among HIV-infected individuals, and the HIV community at-large, to pursue an HIV cure and remission strategies. The potential adverse effects, stigmatization and financial costs encountered by HIV-infected persons receiving life-long antiretroviral therapy along with the potential harm of persistent immune activation/inflammation are strong reasons to pursue HIV cure and remission research. In short, an HIV cure or sustained remission off therapy remain desirable goals that would have substantial benefits for many individuals if achieved.

In recognizing the risk of irAEs with the use of ICIs in the proposed study population and no immediate clinical benefit as previously seen in the setting of cancer treatment, we have attempted to mitigate risk to potential participants to the greatest degree possible. The proposed study will enroll HIV-infected participants with well-controlled HIV-1 viremia on ART and high CD4+ T cell counts without acute illness or malignancy, following a thoughtfully designed and supported dose escalation protocol with close clinical and laboratory monitoring. Risk mitigation related to study drug includes: dose

escalation starting with a dose lower than normally used in the oncology dose escalation studies; and limiting treatment to only two doses of cemiplimab versus placebo separated by 6 weeks to allow for extended safety monitoring prior to the second dose, compared with ongoing every-2-weeks dosing in cancer studies. Eligibility criteria exclude individuals with an increased risk for an irAE including but not limited to: history of an autoimmune disorder, pneumonitis, asthma, diabetes or pre-existing conditions that could make detection or attribution of a potential irAE difficult (e.g., chronic obstructive pulmonary disease [COPD]), the presence of select pre-existing auto-antibodies, or current or history of endocrine disorders. Building upon substantial experience in the cancer studies, we have adapted guidelines for toxicity management of irAEs to ensure prompt detection, appropriate management, and discontinuation of study drug in the event of an irAE.

#### *Summary*

The primary goal of this study is: 1) to test the safety of two doses of cemiplimab versus placebo in a dose rising fashion in participants on suppressive cART, and 2) to determine whether cemiplimab can improve HIV-1-specific cellular immune responses. In addition, we will evaluate the PK of cemiplimab in serum, and examine the time course of RO in whole blood. We plan to simultaneously measure and assess the impact of cemiplimab on: 1) HIV-1-specific T cell magnitude and function, 2) persistent viremia by SCA, and 3) additional measures of HIV-1 persistence in total CD4+ T cells from peripheral blood. Given that only a subset of cancer patients have responded to blockade of the PD-1/PD-L1 pathway in previous clinical trials, we will also explore whether ex vivo response to gag peptides in the presence of cemiplimab pre-treatment is associated with an in vivo response, to identify biomarker(s) predictive of a response to cemiplimab that could inform patient stratification in future studies [33].

If the goals of the study are achieved, the potential next steps would be a larger phase II multiple-dose study of cemiplimab, to further assess safety, HIV specific immune responses, and the impact on HIV reservoirs in blood and tissue, or studies in combination with latency reversing agents or HIV vaccines.

### 3.0 STUDY DESIGN

This trial is a phase I/II, double-blinded (within each cohort), dose-escalating, placebo-controlled study of the safety and immunotherapeutic activity of two infusions of anti-PD-1 (cemiplimab) or placebo in HIV-1-infected participants on cART who have HIV-1 RNA below the limit of quantification and CD4+ T-cell counts  $\geq 350/\text{mm}^3$ . Cemiplimab (0.3 mg/kg [Cohort 1], 1 mg/kg [Cohort 2], and 3 mg/kg [Cohort 3]) or placebo will be given to 15 participants in each Cohort (12 active and 3 placebo). Participants will receive infusions of antibody or placebo at entry/day 0 and week 6, for a total of two infusions, with the primary safety endpoint through week 48 and the primary immunologic endpoint through week 12. The study will enroll sequential dose-escalating cohorts with the second and third cohorts receiving the first infusion after all participants in the previous cohort have reached week 12 and an evaluation of safety outcomes by the study team and the study monitoring committee (SMC) is completed, which determines whether to

dose escalate or not. Participants will be followed for 48 weeks with frequent safety evaluations.

Cemiplimab/placebo infusion will occur over 30 minutes via IV infusion. Safety data from Cohort 1 (first dose level) will be reviewed by the core team (blinded to treatment assignment) and an SMC, before higher doses are administered. Guidance criteria for the SMC with respect to dose escalation are described in [section 10.4.1](#). If the first dose level is well tolerated and the core team and SMC note no safety concerns, Cohort 2 will be enrolled after Cohort 1 reaches week 12. If the second dose level is well tolerated and the core team and SMC note no safety concerns, Cohort 3 will be enrolled after Cohort 2 reaches week 12. Immunologic and virologic response data from lower dose cohort(s) may not be available prior to the enrollment of the subsequent dose cohort(s).

#### 4.0 SELECTION AND ENROLLMENT OF PARTICIPANTS

##### 4.1 Inclusion Criteria

- 4.1.1 HIV-1 infection, documented by any licensed rapid HIV test or HIV enzyme or chemiluminescence immunoassay (E/CIA) test kit at any time prior to study entry and confirmed by a licensed Western blot or a second antibody test by a method other than the initial rapid HIV and/or E/CIA, or by HIV-1 antigen, plasma HIV-1 RNA viral assay.

NOTE: The term “licensed” refers to a US FDA-approved kit, which is required for all IND studies.

WHO (World Health Organization) and CDC (Centers for Disease Control and Prevention) guidelines mandate that confirmation of the initial test result must use a test that is different from the one used for the initial assessment. A reactive initial rapid test should be confirmed by either another type of rapid assay or an E/CIA that is based on a different antigen preparation and/or different test principle (e.g., indirect versus competitive), or a Western blot or a plasma HIV-1 RNA viral load (VL).

- 4.1.2 On ART for at least 24 months prior to screening.

- 4.1.3 Receiving a stable cART regimen (defined as no changes of the components of ART agents within 90 days prior to study entry) containing:

- 1) at least three ART agents (not counting ritonavir if not more than 200 mg total daily dose or cobicistat as one of the agents).

NOTE: One of the agents must include an integrase inhibitor, NNRTI (Non-Nucleoside Reverse Transcriptase Inhibitors), or a boosted-PI (protease inhibitor).

OR

2) two ART agents in which one of the agents is either a boosted protease inhibitor or an integrase inhibitor and the 2-drug regimen is listed as an acceptable alternative regimen in the Department of Health and Human Services guidelines  
(<https://aidsinfo.nih.gov/contentfiles/lvguidelines/adultandadolescentgl.pdf>.)

NOTE: Changes within treatment class, in drug formulation or dose are allowed >30 days prior to study entry (e.g., dolutegravir or elvitegravir to bictegravir, TDF to TAF, ritonavir to cobicistat, or separate ART agent dosing to fixed-dose combination).

4.1.4 CD4+ T cell count  $\geq 350$  cells/mm $^3$  obtained within 90 days prior to study entry at any US laboratory that has a Clinical Laboratory Improvement Amendments (CLIA) certification or its equivalent.

4.1.5 At least two documented plasma HIV-1 RNA below quantifiable limit on cART obtained by FDA-approved assays by any US laboratory that has a CLIA certification or its equivalent within 18 months prior to screening HIV RNA (section 4.1.6).

NOTE: A single unconfirmed plasma HIV-1 RNA  $\geq$  limit of quantification but <1000 copies/mL is allowed if followed by HIV-1 RNA below quantifiable limits.

4.1.6 Plasma HIV-1 RNA level that is less than the quantification limit of an FDA-approved HIV RNA assay within 90 days prior to study entry by any US laboratory that has a CLIA certification or its equivalent.

4.1.7 The following laboratory values obtained within 90 days prior to entry by any US laboratory that has a CLIA certification or its equivalent.

- Absolute neutrophil count (ANC)  $\geq 1500$  cells/mm $^3$
- Hemoglobin  $\geq 14.0$  g/dL for men and  $\geq 12.0$  g/dL for women
- Platelet count  $\geq 150,000/\text{mm}^3$
- Creatinine clearance  $\geq 60$  mL/min estimated by the Cockcroft-Gault equation

NOTE: A program for calculating creatinine clearance by the Cockcroft-Gault method is available on [www.frontierscience.org](http://www.frontierscience.org).

- Alanine aminotransferase (ALT) (SGPT)  $\leq$  upper limit of normal (ULN)
- Aspartate aminotransferase (AST) (SGOT)  $\leq$  ULN
- AM cortisol  $> 10$  mcg/dL and  $<$  ULN

NOTE A: Female participants on estrogen-containing oral contraception or other exogenous estrogen treatment may repeat the AM cortisol as part of screening to determine eligibility. AM cortisol should be drawn as early as possible before 9:00AM, and should not be drawn later than 10:00 AM.

NOTE B: Participants with a low cortisol level that was drawn after 10:00 AM may repeat the AM cortisol as part of screening to determine eligibility.

- Thyroid stimulating hormone (TSH) within normal limits
- Free thyroxine (T4) level within normal limits
- Hemoglobin A1c (HgbA1c) <5.7%
- Fasting blood glucose <110 mg/dL
- Total bilirubin  $\leq 1.6 \times$  ULN

NOTE: If the participant is on an atazanavir-containing therapy then a direct bilirubin should be measured instead of the total bilirubin and must be  $\leq 1.0$  mg/dL.

4.1.8 Interferon-gamma release assay (IGRA) for tuberculosis (TB) with negative results within 90 days prior to study entry, OR

Prior positive TB IGRA or positive purified protein derivative (PPD) skin test with documented evidence of completed prophylaxis treatment (NOTE: IGRA does not need to be repeated at screening). These potential participants cannot have had TB exposure or have traveled to a TB-endemic area since completing prophylaxis treatment. A list of countries with high TB burden is accessible via the following link:

[http://www.who.int/tb/publications/global\\_report/high\\_tb\\_burdenCountrylists2016-2020.pdf](http://www.who.int/tb/publications/global_report/high_tb_burdenCountrylists2016-2020.pdf).

4.1.9 HCV antibody negative result within 60 days prior to study entry or, if the participant is HCV antibody positive, undetectable HCV RNA result within 60 days prior to study entry.

4.1.10 Negative HBsAg result obtained within 60 days prior to study entry.

4.1.11 Negative results for all of the following antibody tests at screening: thyroid peroxidase (TPO), glutamic acid decarboxylase 65 (GAD65/GAD), and islet cell antigen.

4.1.12 Antinuclear antibody (ANA) <1:80 at screening.

4.1.13 Men and women age  $\geq 18$  years and  $< 65$  years.

- 4.1.14 Documentation of the availability of the stored pre-entry plasma specimens for virology assays and stored pre-entry peripheral blood mononuclear cell (PBMC) specimens for CD8+ T-cell assays. Sites must receive confirmation from the processing lab via phone, e-mail, or fax, that specimens have been entered into the ACTG's Laboratory Data Management System (LDMS).
- 4.1.15 Ability and willingness of participant to provide informed consent.
- 4.1.16 Ability and willingness of participant to continue cART throughout the study.
- 4.1.17 In the opinion of the site investigator, the ability to construct a fully active alternative cART regimen in the event of virologic failure on the current ART regimen.
- 4.1.18 Female participants of reproductive potential (defined as women who have not been post-menopausal for at least 24 consecutive months, i.e., who have had menses within the preceding 24 months, or women who have not undergone surgical sterilization, specifically hysterectomy and/or bilateral oophorectomy or bilateral salpingectomy) must have a negative serum pregnancy test with a sensitivity of at least 25 mIU/mL performed at screening, and a serum or urine pregnancy test within 48 hours prior to study entry.
- 4.1.19 All participants must agree not to participate in a conception process (e.g., active attempt to become pregnant or to impregnate, sperm donation, in vitro fertilization, egg donation) during the study.
- 4.1.20 When participating in sexual activity that could lead to pregnancy, all participants must agree to use at least two reliable forms of contraception simultaneously during the study (i.e., entry through week 48). Such methods include:
  - Condoms (male or female) with or without a spermicidal agent
  - Diaphragm or cervical cap with spermicide
  - Intrauterine device (IUD)
  - Tubal ligation
  - Hormone-based contraceptive
- 4.1.21 Participants who are not of reproductive potential (women who have been post-menopausal for at least 24 consecutive months or have undergone hysterectomy and/or bilateral oophorectomy or salpingectomy or men who have documented azoospermia or undergone vasectomy) are eligible without requiring the use of contraceptives. Acceptable documentation of sterilization and menopause is specified below.

Written or oral documentation communicated by clinician or clinician's staff of one of the following:

- Physician report/letter
- Operative report or other source documentation in the patient record (a laboratory report of azoospermia is required to document successful vasectomy)
- Discharge summary
- Follicle stimulating hormone-release factor (FSH) measurement elevated into the menopausal range as established by the reporting laboratory

4.1.22 Weight  $\geq$ 50 kg

4.2 Exclusion Criteria

4.2.1 History of malignancy within the last 5 years.

NOTE: A history of non-melanoma skin cancer (e.g., basal cell carcinoma or squamous cell skin cancer) is not exclusionary with documentation of complete resection at least 3 months prior to enrollment).

4.2.2 History of HIV-related opportunistic infections within the last 5 years prior to study entry.

NOTE: The CDC classifications are available on the A5370 PSWP.

4.2.3 Prior history of immune reconstitution syndrome (IRIS), including a clinical diagnosis of IRIS and/or IRIS requiring intervention (e.g., steroids).

4.2.4 Current chronic, acute, or recurrent bacterial, fungal or viral (other than HIV) infections that are serious, in the opinion of the site investigator, and required systemic therapy within 30 days prior to entry.

4.2.5 History of COPD.

4.2.6 History of prior radiation therapy.

4.2.7 Active or previously treated active TB.

4.2.8 Active asthma requiring any treatment in the prior 2 years, including "as needed" inhaler use prior to study entry.

4.2.9 Type I or type II diabetes mellitus.

4.2.10 History of or active autoimmune disorders including but not limited to inflammatory bowel diseases, scleroderma, severe psoriasis, myocarditis, uveitis, pneumonitis, systemic lupus erythematosus, rheumatoid arthritis, optic neuritis,

myasthenia gravis, adrenal insufficiency, hypothyroidism and/or hyperthyroidism, autoimmune thyroiditis, hypophysitis, or sarcoidosis.

NOTE: For questions related to the definition of autoimmune disorders, sites should contact the team per the [Study Management](#) section.

- 4.2.11 Immune deficiency other than that caused by HIV infection.
- 4.2.12 Currently breastfeeding or pregnant.
- 4.2.13 Known allergy/sensitivity or any hypersensitivity to mAb-based biologics, cemiplimab (anti-PD-1) or its formulation.
- 4.2.14 Active drug or alcohol use or dependence that, in the opinion of the site investigator, would interfere with adherence to study requirements.
- 4.2.15 Received investigational drug or device within 6 months prior to study entry.
- 4.2.16 Use of immunomodulators (e.g., interleukins, interferons, cyclosporine, systemic corticosteroids exceeding physiologic doses), HIV vaccine, or systemic cytotoxic chemotherapy within 60 days prior to study entry.

NOTE: Participants receiving stable physiologic glucocorticoid doses, defined as prednisone  $\leq$ 10 mg/day or the equivalent, will not be excluded. Stable physiologic glucocorticoid doses should not be discontinued for the duration of the study. In addition, participants receiving topical corticosteroids will not be excluded.

- 4.2.17 Intent to use immunomodulators (e.g., IL-2, IL-12, interferons, systemic corticosteroids exceeding physiologic doses, or TNF modifiers) during the course of the study.
- 4.2.18 Any vaccination within 30 days prior to pre-entry or entry.

NOTE: Individuals who require vaccination will delay screening for the study until 30 days after receiving the last injection.

- 4.2.19 HCV treatment within 6 months prior to study entry.
- 4.2.20 Any acute or chronic psychiatric problems that, in the opinion of the investigator, make the participant ineligible for participation.
- 4.2.21 History of solid organ transplant.

NOTE: Participants with prior corneal transplant(s) may be allowed to enroll after discussion with and approval from the study medical officer.

- 4.2.22 History of previous treatment with a phosphoinositide 3-kinase inhibitor, including idelalisib.
- 4.2.23 History of prior checkpoint inhibitor treatment including anti-PD-1, anti-PD-L1 or anti-CTLA-4 antibodies (including ipilimumab).
- 4.2.24 History of prior immunoglobulin (IgG) therapy.
- 4.2.25 Current use or intent to use biotin  $\geq$ 5 mg/day, including within dietary supplements during the study.

NOTE: Please see [section 5.4](#) for a list of other names used for biotin that should be looked for on the labels of dietary supplements.

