### 1.3 Secondary Objectives

- 1.3.1 To evaluate the change in magnitude of HIV-1 gag-specific CD8+ T cells by intracellular staining for both CD107a and interferon gamma (IFN- $\gamma$ ) from a pre-treatment baseline level (average of 2 measurements) to time points after one or two doses of cemiplimab (average of responses from weeks 2, 4, 6, 8, 10, and 12).
- 1.3.2 To evaluate the change in magnitude of HIV-1 gag-specific CD8+ T cell responses using both CD107a and IFN- $\gamma$  expression from baseline to time points after the first dose of cemiplimab or placebo (average of responses from weeks 2, 4, and 6), and to time points after the second dose or placebo (average of responses from weeks 8, 10, and 12).
- 1.3.3 To evaluate the change in magnitude of HIV-1 gag-specific CD8+ T cells by intracellular staining for IFN- $\gamma$  or CD107a alone, from baseline (pre-treatment average) to time points after one or two sequential doses of cemiplimab or placebo (average of responses from weeks 2, 4, 6, 8, 10, and 12) and explore difference following each dose.
- 1.3.4 To evaluate changes in polyfunctional response of HIV-1-gag-specific CD8+ T cells by intracellular staining for IFN- $\gamma$ , CD107a, IL-2, and TNF $\alpha$  from baseline (pre-treatment average) to time points after one or two sequential doses of cemiplimab or placebo and explore difference following each dose.
- 1.3.5 To assess the durability of response to cemiplimab by evaluating the magnitude of HIV-1 gag-specific CD8+ T cell responses by intracellular staining of CD107a and IFN- $\gamma$  and polyfunctional response through week 48.

1.3.6 To assess immunogenicity to cemiplimab after multi-dose administration to cART-treated HIV-1-infected participants.

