#### Pre-Entry

Pre-entry evaluations must be completed 30-50 days prior to entry evaluations unless otherwise specified.

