#### 6.3.2 Medical History

The medical history must include all signs and symptoms regardless of grade and all diagnoses identified by the ACTG criteria for clinical events and other diagnoses regardless of grade within the past 30 days. In addition, the following diagnoses should be recorded regardless of when the diagnosis was made:

- AIDS-defining conditions
- Bone fractures (verbal history accepted)
- Coronary heart disease
- Cancer (exclusive of basal/squamous cell skin cancer)
- Diabetes
- Asthma
- Tuberculosis
- Chronic hepatitis C
- Chronic hepatitis B

Any allergies to any medications and their formulations must also be documented.

Document the pre-ART HIV-1 RNA level and nadir CD4 count if available. If pre-ART nadir CD4 count documentation or pre-ART HIV RNA level is not available, then collect and record participant recall. Document date of first undetectable HIV-1 RNA level prior to sustained VL suppression (may be estimated if exact date not available) and the date(s) of any previous virologic failure on ART.

The medical history evaluation will be assessed at the screening and entry visit and recorded on the eCRFs at the study entry visit.

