### 10.6.2 Secondary Analyses

For the HIV-1-specific CD8+ T cell efficacy outcome ([section 10.2.2.1](#)), post-treatment changes will be evaluated, comparing measurements at baseline (averaging the pre-treatment measures) to an average of post-treatment measurements through week 12, jointly analyzing the actively treated participants from all dose cohorts using the paired t-test. As supplemental analyses, the

same methods will separately analyze each dose cohort. The rationale to average over multiple post-treatment timepoints is that the timing and dynamics of treatment-induced immunologic (or virologic) effects is not known; the average of multiple time points aims to capture both early effects that may wane (for example, as seen in one of the immunologic responders to a single-dose of the anti-PD-L1 antibody [26]; or, for example, a response that only appears following the second infusion). Graphical approaches will display the means at each visit and mean changes from baseline to each follow-up visit (and separately to the average of weeks 2-6 and to weeks 8-12), by dose cohort and separately for the placebo participants. Longitudinal participant-specific plots will also be presented for each treatment dose and for the placebo participants.

Because the aim of this phase I/II study is to investigate the biologic effects of the treatment (anti-PD-1 antibody cemiplimab), efficacy analyses will be “as-treated” and also, to maximize the ability to identify treatment effects, efficacy analyses will be based only on participants who completed  $\geq 90\%$  of both study treatment infusions. In addition, if any participant interrupts cART for more than 7 consecutive days during the study, only measurements prior to cART interruption will be used in efficacy analyses.

Analyses of other immunologic and virologic measures will parallel the efficacy analyses as outlined above. For example, cell-associated HIV-1 RNA levels will be compared pre-treatment to post-treatment using paired t-tests separately by dose group (and for the combined treated participants) and for the placebo participants. Virologic measures such as cell-associated HIV-1 RNA will be log-transformed prior to analyses. Because low-level viremia as measured by SCA is anticipated to be below assay limit in a substantial fraction (~50%) of participants, binary (GEE) or censored-data [64] longitudinal analysis approaches are planned to assess treatment effects on SCA.

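### The infection and immunomodulator exclusions (4.2.4, 4.2.16) count back from entry only, so they protect the pre-entry half of the CD8+ baseline poorly or not at all; the likely effect is modest and the fix is cheap

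*Protocol*

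**What the plan says.** Three exclusion criteria in Protocol 4.2 set a look-back for exposures that can disturb immune measurements, with two different anchors.

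- 4.2.4 covers "infections that are serious, in the opinion of the site investigator, and required systemic therapy within 30 days prior to entry". The anchor is entry.
- 4.2.16 covers immunomodulators, "HIV vaccine, or systemic cytotoxic chemotherapy within 60 days prior to study entry". The anchor is entry.
- 4.2.18 covers "Any vaccination within 30 days prior to pre-entry or entry". The anchor is pre-entry as well as entry.

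On timing, section 6.2.2 says "Pre-entry evaluations must be completed 30-50 days prior to entry evaluations unless otherwise specified".

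On the use of that visit, objective 1.3.1 measures change "from a pre-treatment baseline level (average of 2 measurements", closing bracket omitted. Criterion 4.1.14 makes documented availability of "stored pre-entry peripheral blood mononuclear cell (PBMC) specimens for CD8+ T-cell assays" a condition of enrolment, and the schedule of evaluations marks the immunology sample at pre-entry and at entry. Section 10.6.2 analyses the outcome by "comparing measurements at baseline (averaging the pre-treatment measures) to an average of post-treatment measurements through week 12", with a paired t-test in actively treated participants. Section 10.4.2 states the assumption behind that test: mean change is zero without the intervention.

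**The concern.** 4.2.18 protects the pre-entry sample from a recent immune stimulus; 4.2.4 and 4.2.16 do not, although a treated serious infection or a recent immunosuppressant could also disturb a T-cell measurement. The main efficacy test has no concurrent control in it, so a displaced baseline is not differenced out. A pre-entry value raised by infection makes the later change look smaller and costs power. A value lowered by an immunosuppressive agent makes an unchanged response look like an increase. A stored baseline sample cannot be redrawn after dosing.

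The diagnosis record does not fill the gap by itself. Section 6.3.2 asks for "other diagnoses regardless of grade within the past 30 days", assessed at screening and entry. Screening is on day -90 to -60 and the entry look-back reaches day -30, so an infection on day -45 can fall between the two.

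**Working it through.** **1. The plan's own figures (10.4.2).** Paired t-test, two-sided alpha 0.05, noncentrality = d × √n, n − 1 degrees of freedom.
- n = 11, d = 0.94: noncentrality 3.12, power 0.802; Φ(0.94) = 0.83.
- n = 33, d = 0.504: noncentrality 2.90, power 0.802; Φ(0.504) = 0.69.

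Both agree with the stated power above 80% and the stated probabilities 0.83 and 0.69. They are not in dispute and serve only as the yardstick.

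**2. Date arithmetic (entry = day 0; pre-entry draw on day -50 to -30).**

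| Criterion | Last permitted exposure | Draw on day -50 | Draw on day -30 |
|---|---|---|---|
| 4.2.4, 30 days from entry | day -31 | therapy may be under way | covered |
| 4.2.16, 60 days from entry | day -61 (day -60 if the bound is exclusive) | 61 − 50 = 11 (or 10) days clear | 61 − 30 = 31 (or 30) days clear |
| 4.2.18, 30 days from pre-entry or entry | 30 days before the draw | 30 days clear | 30 days clear |

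For infection therapy, 20 of the 21 permitted draw days (-50 to -31) are uncovered. No eligible participant can be taking a 4.2.16 agent at the draw itself; only the washout is shortened.

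**3. Other text that might close the gap.** 4.2.17 looks forward only. The prohibited-medication list (5.4.2) sets no pre-entry washout for immunomodulators and does not cover anti-infective therapy. Neither protects the pre-entry draw.

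**4. How an error enters the change.** Change = mean(post) − (pre-entry + entry)/2, so a shift of s in the pre-entry value moves that participant's change by s/2. In relative terms, with an unchanged response and the pre-entry value multiplied by m, the post/baseline ratio is 2/(m + 1). A doubled value gives 2/3 (an apparent −33%), a halved one 2/1.5 = 4/3 (an apparent +33%). These multiples are illustrations.

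**5. Size under an assumption.** The documents give no frequency and no shift size. Let k participants have the pre-entry value shifted in the same direction by s, in SD-of-change units. The mean change moves by k × s/(2n).

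| | k = 1, s = 1 | k = 1, s = 2 | k = 3, s = 1 | k = 3, s = 2 |
|---|---|---|---|---|
| n = 33 (detectable 0.504) | 0.015 | 0.030 | 0.045 | 0.091 |
| n = 11 (detectable 0.94) | 0.045 | 0.091 | 0.136 | 0.273 |

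Pooled, this is 0.015/0.504 = 3% to 0.091/0.504 = 18% of the detectable effect. The upper end needs three affected participants, all shifted the same way by 2 SD.

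**The case against.** Several counter-arguments carry weight.

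- **Visibility.** Section 6.3.3 requires a medication history updated at entry with start and stop dates, and a complete history of immune-based therapy. The concomitant-medication part of 6.3.4 records, at entry, drugs new or discontinued since the last visit. Anti-infective therapy under way at pre-entry and stopped before entry should therefore be recorded. This stands: most affected samples can be identified, though 10.6.2 gives no rule for using the information.
- **Rarity.** Participants have CD4+ counts of at least 350 and suppressed HIV, and much comorbidity is excluded. Few are likely to be affected. This stands.
- **Purpose.** An entry anchor is natural for criteria that also protect participants at dosing, and safety is the primary objective. Vaccination also has its own rule in 5.4.2, tied to every study visit, so 4.2.18 is not firm proof of an oversight. This weakens the inference about intent, but the baseline sample is still unprotected.
- **Stakes.** The outcome is secondary, the entry draw is covered by both windows, and placebo participants are displayed on the same schedule, which gives a limited check.

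A reader might go further and infer that the gap materially inflates the type I error. In a simulation of the pooled test (n = 33, pre-entry value shifted by 2 SD in a fraction f), two-sided type I error does rise to about 6% (f = 5%), 8% (f = 10%) and 17–18% (f = 20%) if every shift is downward. The documents do not support that reading. They give no source for f or for the 2 SD shift. Uniformly downward shifts would have to come from immunomodulators alone, whose washout is shortened but not absent. If infection raises the value, false increases become rarer (from 2.5% to about 0.6% at f = 10%), and the cost is power: from 80% to about 69% at f = 5% and 58% at f = 10%. With shifts of random sign the error stays near 5%.

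**Conclusion.** The anchors are inconsistent, and the pre-entry half of the CD8+ baseline is not protected from treated serious infection (days -50 to -31) and only briefly from immunomodulators (10–11 to 30–31 days). The text supports that much without any assumption.

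The consequence is probably modest and its direction depends on the exposure: lost power if the pre-entry value is raised, an apparent increase if it is lowered. The range of 0.015 to 0.09 SD on the pooled mean change rests on 1 to 3 affected participants and a 1 to 2 SD shift, neither of which the documents supply. It would also be too strong to say that such exposures go unrecorded: the diagnosis may be missed, but the drug usually is not. Sample size, power and the primary safety analysis are unaffected. This is a minor point, worth considering because the correction is cheap.

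**What to change.** Either of two changes is enough.

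1. Reconcile the anchors: let 4.2.4 and 4.2.16 count their existing 30 and 60 days back from pre-entry or entry, as 4.2.18 does. The guaranteed clear interval before the pre-entry draw becomes 30 days for infection therapy (now 0) and 60 days for immunomodulators (now 10–11 at the shortest). Cost: a few words in two criteria, and a few candidates whose pre-entry visit is delayed.
2. Leave eligibility as it is and add one sentence to 10.6.2: when therapy for such an infection, or such an agent, falls within the stated window before the pre-entry draw, the entry draw alone is the baseline. The drug records under 6.3.3 and 6.3.4 should usually identify these participants. Cost: a single-sample, noisier baseline for a few participants.

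Neither changes the sample size, the visits or the dosing.
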